7.6.6 Treatment Response by Subsets

For all randomized patients, the objective response rate will be presented for each treatment arm in the subgroups defined by the categorical variables listed below (**Table 40**). No formal comparisons are planned:

- gender (male, female)
- age (<65 years, ≥65 years)
- race (white, black, other)
- performance status at baseline (ECOG 0, ECOG 1)
- Site of tumour (right colon, transverse colon, left colon, rectum)
- KRAS status (wildtype, mutated)
- NRAS status (wildtype, mutated)
- BRAF status (wildtype, mutated)
- MSI status (MSI-H, MSI-L, MSS)

7.6.7 Duration of Response

For patients whose best responses are classified as CR or PR at any reporting period during the study, the duration of response is calculated as the time from CR or PR is documented (whichever is the first) until first observation of objective disease relapse or progression or death due to any cause. If a patient has not relapsed/progressed or died, duration of response will be censored on the date of last disease assessment defined as the earliest test date of target lesion or non-target lesions (if patient has no target lesions), whichever is latest.

All randomized patients with CR or PR are included in this analysis. The median duration of response and associated 95% confidence intervals will be computed and compared by the stratified log-rank test adjusting for stratification factors at randomization (**Table 41**).

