13.3 Sample Size and Duration of Study

The study is designed to have a power of 80% and a two-sided alpha of 10% to detect a 35% reduction in the continuous risk of death (HR 0.65, which corresponds to an increase of median survival from 4.5 to 6.9 months). It is estimated that 150 events will be required to detect this reduction. The final analysis will be performed when 150 events are observed. Assuming an accrual rate of around 10 patients per month, the required number of events would be observed by accruing a total of 180 patients and following them for a minimum of 6 months. The total duration of the trial would be around 24 months.

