2.1 Study Design

Study CCTG CO.26 is a multi-centre, open-label, randomized phase II trial of durvalumab and tremelimumab combined with best supportive care *versus* best supportive care alone (where best supportive care is defined as those measures

designed to provide palliation of symptoms and improve quality of life as much as possible) in patients with refractory, advanced colorectal carcinoma. Patients are stratified by ECOG performance status (0 vs. 1) and site of tumour (right colon vs. transverse colon vs. left colon vs. rectum vs. unknown) prior to randomization. This study is conducted by CCTG with support from AstraZeneca. CCTG Case Report Forms (CRFs) are used and the database are maintained by CCTG.

A total of 180 patients would be enrolled (120 on Durva+Treme and 60 on BSC). The final analyses will be performed by CCTG when the required number of deaths (150) is recorded. This analysis plan describes the analyses performed at the completion of the study.

This study was activated on August 10, 2016 and closed to randomization of patients on June 29, 2017 after 180 patients were randomized. The CCTG Data Safety Monitoring Committee has been reviewing safety data every six months (usually at the time of the bi-annual CCTG Spring and Fall meetings) and as otherwise required. These analyses have been prepared by a CCTG/Queen's Senior Biostatistician.

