2.2 Treatment Allocation

The study is planned to randomize 180 subjects using a 2:1 allocation to durvalumab and tremelimumab combined with best supportive care (Durva+Treme Arm or ARM 2) and best supportive care alone (BSC Arm or ARM 1). The randomization was dynamically balanced by ECOG performance status (0 vs. 1) and site of tumour (right colon vs. transverse colon vs. left colon vs. rectum vs. unknown) using the method of minimization. A centralized system was used to randomize all patients in this study.

3. Objectives

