7.1 General Methods

All comparisons between treatment arms will be carried out using a two-sided test at an alpha level of 10% unless otherwise specified.

When appropriate, discrete variables are summarized with the number and proportion of subjects falling into each category, and compared using Fisher's exact test. Continuous and ordinal categorical variables are summarized using the mean, median, standard error, minimum and maximum values and when appropriate, compared using the Wilcoxon test. All confidence intervals are computed based on normal approximations except those for rates, which will be computed based on the exact method.

Time to event variables are summarized using Kaplan-Meier plots. Primary comparisons of the treatment groups are made using the stratified log-rank test. Primary estimates of the treatment differences are obtained with the hazard ratios and 90% confidence intervals from stratified Cox regression models using treatment arm as the single factor.

Percentages given in the summary tables will be rounded and may therefore not always add up to exactly 100%. Listings, tabulations, and statistical analyses will be carried out using the SAS (Statistical Analysis System, SAS Institute, North Carolina, USA) software.

Unless otherwise specified, date of randomization and stratification factors will be taken from the Centralized Randomization File.

Baseline evaluations will be those collected on Eligibility Checklist and Baseline Report and closest to, but no later than, the first day of study medication for treated subjects and closest to, but no later than, the date of randomization, for subjects who were randomized but who never received treatment.

Laboratory results, adverse events, and other symptoms are coded and graded using the Common Terminology Criteria for Adverse Events (CTCAE v4.0).

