Treatment arm DURVA+TREME: BSC	**.* (**.*; **.*)	0.***	**.* (**.*; **.*)	0.***
Gender Male: Female	NC ⁽³⁾	0.***	**.* (**.*; **.*)	0.***
Age <65: ≥65	NC	0.***	**.* (**.*; **.*)	0.***
Number of organ sites ≤2: >2	NC	0.***	**.* (**.*; **.*)	0.***
Number of previous chemo drug classes ≤2: >2	NC	0.***	**.* (**.*; **.*)	0.***
Presence of liver metastases No: Yes	NC	0.***	**.* (**.*; **.*)	0.***

(1) Stratified

(2) Stratified Logistic regression, all factors included

(3) NC = not computed

(4) Odds ratio of first category over second category

Table 40: Response According to Pretreatment Characteristics

Data set: All Randomized Patients		
	Number of Responses/Number of Patients (%)	
	DURVA+TREME N=***	BSC N=***
Gender		
Male	**/** (**)	**/** (**)
Female	**/** (**)	**/** (**)
Age		
< 65 years	**/** (**)	**/** (**)
≥ 65 years	**/** (**)	**/** (**)
Race		
White	**/** (**)	**/** (**)
Black	**/** (**)	**/** (**)
Other	**/** (**)	**/** (**)
Baseline performance status		
ECOG 0-1	**/** (**)	**/** (**)
ECOG 2	**/** (**)	**/** (**)
Site of Tumour		
Right colon	**/** (**)	**/** (**)
Transverse colon	**/** (**)	**/** (**)
Left colon	**/** (**)	**/** (**)
Rectum	**/** (**)	**/** (**)
KRAS status		
Wildtype	**/** (**)	**/** (**)
Mutated	**/** (**)	**/** (**)
NRAS status		
Wildtype	**/** (**)	**/** (**)
Mutated	**/** (**)	**/** (**)
BRAF status		
Wildtype	**/** (**)	**/** (**)
Mutated	**/** (**)	**/** (**)
MSI status		
MSI-H	**/** (**)	**/** (**)
MSI-L	**/** (**)	**/** (**)
MSS	**/** (**)	**/** (**)

Table 41: Duration of Response

Data set: All Randomized Patients with CR or PR			
	DURVA+TREME N=***	BSC N=***	P-value ⁽¹⁾
Median Duration of Response (months) (90% CI)	*** (**_**)	*** (**_**)	.**

(1) Stratified

Table 42: Adverse Events on Durvalumab and Tremelimumab Treatment

Data set: All Treated Patients on DURVA+TREME Arm							
	Number of patients (%) N=***						
	Worst grade						Any grade
	NR	1	2	3	4	5	
Patients with any AE	** (**)	** (**)	** (**)	** (**)	** (**)	** (**)	** (**)
Patients with AE within category							
Category 1 ⁽¹⁾	** (**)	** (**)	** (**)	** (**)	** (**)	** (**)	** (**)
Event 1	** (**)	** (**)	** (**)	** (**)	** (**)	** (**)	** (**)
Event 2	** (**)	** (**)	** (**)	** (**)	** (**)	** (**)	** (**)
Event 3	** (**)	** (**)	** (**)	** (**)	** (**)	** (**)	** (**)
...							

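### Duration of response is tested between arms among responders only (SAP 7.6.7, Table 41), so its p-value is not a randomised comparison and may rest on one BSC responder or none

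*SAP*

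**What the plan says.** SAP 7.6.7 fixes the analysis set: "All randomized patients with CR or PR are included in this analysis". On that set it plans a test: "The median duration of response and associated 95% confidence intervals will be computed and compared by the stratified log-rank test", with the randomisation factors as strata. No level is given there, so SAP 7.1 supplies it: "All comparisons between treatment arms will be carried out using a two-sided test at an alpha level of 10% unless otherwise specified".

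Table 41 follows the same plan. Its header is "Data set: All Randomized Patients with CR or PR", its single row is "Median Duration of Response (months) (90% CI"), and it has a column for the stratified p-value.

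Nothing labels this test descriptive. There is no minimum number of responders and no rule for an arm with none. SAP 7.6.6, just before it, rules out formal comparisons, but only for response by subset. Protocol 8.3 defines response duration; Protocol 13.2 plans no comparison of it.

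**The concern.** Whether a patient responds is an outcome of the assigned treatment. If the regimen turns some patients into responders who would not have responded on BSC, the responders in the two arms are different kinds of patient. A difference in duration, or the lack of one, can then come from that selection alone. Randomisation does not protect the comparison at any sample size.

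The second problem is sparse data. BSC is palliation only (Protocol 7.1.1) and has half as many patients as the other arm, so it may produce very few responders. The test would then be spread over ten strata with almost nothing in one arm.

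At stake is one printed p-value that could be cited for or against longer responses. The primary result is not affected.

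**Working it through.** **The plan's own figure.** No responder count or power is stated for duration of response. The only design calculation is for overall survival: "The study is designed to have a power of 80% and a two-sided alpha of 10"%, HR 0.65, 2:1 allocation. Schoenfeld's formula gives (1.645 + 0.842)² / [(2/3)(1/3)(ln 0.65)²] = 6.18 / 0.0412 = 149.9, which agrees with the stated 150 events. This point does not touch that design.

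**Inputs.** Arm sizes: "A total of 180 patients would be enrolled (120 on Durva+Treme and 60 on BSC"). Strata: allocation was "dynamically balanced by ECOG performance status (0 vs. 1) and site of tumour (right colon vs. transverse colon" and three further site levels), so 2 × 5 = 10 cells. The BSC response rate p is not in the documents; the range 0% to 2% is assumed, with 5% shown for contrast.

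**1. How many BSC responders?** P(0) = (1 − p)^60 and P(1) = 60p(1 − p)^59.

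| p | expected | P(0) | P(1) | P(0 or 1) |
|---|---|---|---|---|
| 0% | 0 | 100% | 0% | 100% |
| 1% | 0.6 | 55% | 33% | 88% |
| 2% | 1.2 | 30% | 36% | 66% |
| 5% | 3.0 | 5% | 15% | 19% |

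**2. What the planned test does with so few.** With no BSC responder, everyone at risk at every event time is in one arm, so observed minus expected and the variance are both zero and there is no statistic.

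With one BSC responder, only that patient's cell has a non-zero variance. Let k Durva+Treme responders share the cell, without ties or censoring. If the BSC response ends first, O − E = 1 − 1/(k+1) = k/(k+1), V = k/(k+1)², and Z = √k:

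- k = 1: Z = 1.00, p = 0.32
- k = 2: Z = 1.41, p = 0.16
- k = 3: Z = 1.73, p = 0.083

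Over all orderings, k = 2 gives Z = 1.41, 0.24 and −1.21, so the test cannot reject. For k = 3, Z = 1.73, 0.65, −0.10 and −1.33, so one ordering in four rejects. Whether the test can reject at all depends on which cell one patient falls in.

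**3. Level over the cell mix.** Assumed mix: ECOG 30/70; sites 25/8/37/28/2%. Rejection at nominal 10% with no difference in duration, by fixed responder counts (Durva+Treme versus BSC), untied and uncensored:

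| Counts | Overall | When computable |
|---|---|---|
| 4 v 1 | 0.6% | about 1% |
| 6 v 1 | about 2% | about 3% |
| 8 v 1 | about 4% | about 6% |
| 10 v 1 | about 6% | 7% to 8% |
| 6 v 2 | about 7% | 8% to 9% |
| 8 v 2 | about 10% | about 12% |

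By response rate instead, adding exponential durations with median 6 months and uniform censoring at 3 to 15 months (all assumed; 12,000 runs each):

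| Durva+Treme / BSC | Computable | Rejects when computable | Rejects overall |
|---|---|---|---|
| 5% / 1% | 25% | 5.5% | 1.4% |
| 5% / 2% | 44% | 6.1% | 2.7% |
| 10% / 1% | 34% | 9.4% | 3.2% |
| 10% / 2% | 57% | 11.0% | 6.2% |
| 10% / 5% | 87% | 11.3% | 9.8% |

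**4. Selection.** Let duration correlate with the propensity to respond, with no treatment effect on any patient's duration. At 30% / 10% response and correlation 0.8, rejection when computable was 8.1% or 26.9%, depending on the assumed time scale of the durations. In the second case almost all rejections pointed to shorter duration on Durva+Treme. At 10% / 2% on that same shorter time scale it was 7.1% (correlation 0.5) and 6.7% (correlation 0.8). The size rests wholly on unknown inputs.

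**5. Interval level.** SAP 7.6.7 asks for 95%; Table 41 shows 90%. SAP 7.1 uses 90% for hazard ratios and SAP 7.6.1 uses 90% for median survival.

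**The case against.** The strongest reply is that nothing depends on this test. SAP 4.1 and 4.2 do not name duration of response as an endpoint. Response is compared in all randomised patients by the CMH test (SAP 7.6.5), and time-to-event benefit by OS and PFS in all randomised patients. If BSC has no responders, no p-value can be produced, so no false claim can follow. The BSC response rate is also not in the documents, so the sparse-data argument rests on an assumption. All of this stands, and it limits the point to a minor one.

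A reader might go further and infer that the test inflates the false-positive rate in favour of Durva+Treme, for instance by working out an ordinary log-rank test with several responders against one. The documents do not support that. The SAP plans a stratified test, and a single BSC responder can be compared only with responders in the same cell. At the counts tried in step 3, the planned test is conservative in five of six cases and near nominal in the sixth. Clear inflation appeared only with selection and much higher response rates, which is not the case of few BSC responders.

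The reply does not remove the main point. A responder-only comparison is not a randomised one, and the SAP prints its p-value without a caveat.

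**Conclusion.** The point holds as a minor one. From the text alone it is certain that Table 41 would carry a p-value comparing groups selected by an outcome after randomisation, and that the 95% and 90% interval levels contradict each other.

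Conditional on an assumed BSC response rate of 0% to 2%, zero or one BSC responder has a probability of 66% or more. The test is then undefined or rests on one stratum, and its nominal 10% level cannot be relied on. Without selection, the rates found for the planned test at BSC rates of 1% to 5% run from 1.4% to 9.8% overall and from 5.5% to 11.3% when computable. That is a test that is often conservative or not computable, not one shown to be inflated. These figures also rest on the assumed Durva+Treme response rate, cell mix, durations and censoring.

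**What to change.** In SAP 7.6.7, delete the between-arm log-rank test and change 95% to 90% to match Table 41. In Table 41, delete the p-value column and its footnote. Report by arm, labelled as descriptive: the number of responders, the Kaplan-Meier median duration with its 90% CI, and the range.

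The cost is an edit to one paragraph and one table. The only loss is one p-value for a quantity that is not a named endpoint.

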7.7 Safety

The safety analyses will be based on the All Treated population defined in Section 6. Adverse events and laboratories are graded and categorized using the CTCAE v4.0 criteria except where CTCAE grades are not available.

7.7.1 Adverse Events

Adverse events will be recorded on the CCTG toxicity/adverse event-intercurrent illness case report form. Events reported on Treatment Report or 4-Week Post-Treatment Follow-Up Report for patients on the Durva+Treme arm will be defined as adverse events on Durva+Treme; Events reported on any case report forms except Form 1 will be summarized separately for patients on both arms as overall adverse events during the (whole) study.

Drug related adverse events are those events with a relation to protocol therapy of 3=possible, 4=probable or 5=definite.

Severe adverse events are those events reported with a CTCAE Grade of 3 or higher.

Comparisons between treatment arms on overall adverse events (any vs. other, severe vs. other) will be carried out using a two sided Fisher's exact test at an alpha level of two-sided 10%.

The following variables are summarized. Tabulations of overall adverse events will be presented by treatment group.

- Adverse events on Durva+Treme: worst CTCAE grade per patient (**Table 42**)
- Severe adverse events on Durva+Treme: worst CTCAE grade per patient (**Table 43**)
- Drug related adverse events on Durva+Treme: worst CTCAE grade per patient (**Table 44**)
- Overall adverse events: worst CTCAE grade per patient (**Table 45**)
- Severe overall adverse events: worst CTCAE grade per patient (**Table 46**)

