| Required Investigations | PRE-STUDY (≤14 days prior to randomization, unless otherwise indicated) | DURING Protocol Treatment Day 1 each cycle, and as clinically indicated (unless otherwise indicated) | AFTER Protocol Treatment is Permanently Discontinued ¹ | | | |
|--|--|---|---|--------------------------|---|---------------------------|
| | | | PRIOR to objective disease progression | | AFTER objective disease progression | |
| | | | 4 weeks after end of last cycle date | Every 4 weeks thereafter | 4 weeks after end of last cycle date ¹ | Every 12 weeks thereafter |
| Correlative Studies | | | | | | |
| Archival Tissue Sample ⁹ (mandatory) | Availability of sufficient tissue must be confirmed prior to randomization | Submit tissue within 4 weeks of randomization | | | | |
| Whole blood, plasma and serum ⁹ (mandatory) | After randomization but before first dose of study treatment | To be done at 8 weeks and at the time of objective disease progression ¹⁰ , if not already done | | | | |
| Adverse Events | | | | | | |
| Adverse Event Assessment ¹¹ | X (To document residual adverse events from previous therapy and baseline symptoms) | X ¹² (To be evaluated continuously for adverse events) | X | X ¹³ | X ¹ | X ¹³ |
| Quality of Life | | | | | | |
| EORTC QLQ C30 ¹⁴ | X | At 4, 8, 12, 16 and 24 weeks after randomization, then every 12 weeks thereafter (until deterioration to ECOG PS 4 or hospitalization for end of life care) | | | | |

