7.7.2 Laboratory Evaluations

For patients on Durva+Treme, laboratory evaluations reported on Treatment Report or 4-Week Post-Treatment Follow-Up Report for patients on the Durva+Treme arm will be included in the calculation for laboratory adverse events on Durva+Treme. All laboratory evaluations reported after baseline assessment will be included in the calculation for overall laboratory adverse events. Laboratory results will be classified according to CTCAE version 4.0. Laboratory tests that are not covered by the CTCAE grading system will be summarized according to the following categories: normal and above the upper normal limits.

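### Safety tables count every post-baseline event and laboratory value at worst grade without reference to baseline, which overstates incidence in both arms and dilutes the any-grade adverse event comparison

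*SAP*

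**What the plan says.** SAP 7.7.1 sets two counting rules for adverse events. Anything on a Treatment Report or 4-Week Post-Treatment Follow-Up Report in the Durva+Treme arm is an event on treatment (Tables 42-44). For the whole study, "Events reported on any case report forms except Form 1 will be summarized separately for patients on both arms as overall adverse events" (Tables 45 and 46). Each table shows worst CTCAE grade per patient. Between-arm comparisons of overall events, any versus other and severe versus other, "will be carried out using a two sided Fisher's exact test at an alpha level of two-sided 10" per cent.

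For laboratory tests, SAP 7.7.2 says: "All laboratory evaluations reported after baseline assessment will be included in the calculation for overall laboratory adverse events". Tables 47-54 then give the worst grade or category per patient. No shell has a baseline column or a shift.

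Baseline status is known. The flowsheets in Protocol 5.1 and 5.2 require a pre-study adverse event assessment in both arms; its stated purpose is "To document residual adverse events from previous therapy and baseline symptoms". SAP 7.4.6 tabulates baseline symptoms and laboratory, thyroid and coagulation results in Tables 14-18, and SAP 7.1 defines a baseline evaluation. Neither document links these data to the safety tables, and neither defines a treatment-emergent event.

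**The concern.** Leaving out Form 1, which neither document defines but which is presumably the baseline form, drops the baseline record itself. It does not drop the same symptom written down again at week 4.

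The population makes this matter. These are heavily pretreated patients with refractory disease. Protocol 4.1.21 admits hemoglobin down to 90 g/L, AST and ALT up to 2.5 times the upper limit of normal, and lymphocytes at any value. The SAP's own baseline shells allow hemoglobin grade 2 and grade 4 for lymphocytes and alkaline phosphatase. A patient with stable grade 3 lymphopenia from before randomization would appear in Table 47 as grade 3 during treatment.

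Two things are at stake for the secondary safety objective. The absolute rates are overstated; this is most visible in Tables 42, 43, 47 and 49, which show Arm 2 alone. And where the arms are compared, events common to both at baseline hide part of any real difference.

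**Working it through.** **The plan's own figure.** The only reproducible design figure is for overall survival. Protocol 13.3: "The study is designed to have a power of 80% and a two-sided alpha of 10% to detect a 35% reduction", with "HR 0.65, which corresponds to an increase of median survival from 4.5 to 6.9 months", and "It is estimated that 150 events will be required to detect this reduction". With 2:1 allocation the Schoenfeld formula gives (1.645 + 0.842)² / [(2/3)(1/3)(ln 0.65)²] = 6.18 / 0.0412 = 149.9, or 150 events; and 4.5 / 0.65 = 6.9 months. This reproduces and is untouched by the present point. The documents give no design figure for the adverse event comparison.

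**Inputs.** Arm sizes are from SAP 2.1 ("A total of 180 patients would be enrolled (120 on Durva+Treme and 60 on BSC"); the test and its level are from SAP 7.7.1. The carry-over proportion b and the new-event rates p are not in the documents. They are assumptions, shown as a range.

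**Model.** Let b be the proportion of patients, equal in both arms, with a baseline symptom that is reported again. The reported rate is b + (1 - b)p. Three things follow:
- each arm's rate rises by b(1 - p), so the arm with the lower p rises more;
- the difference between arms becomes (1 - b)(p₂ - p₁), where p₂ is Arm 2 and p₁ is BSC;
- if p₂ = p₁ the reported rates are also equal, so the null hypothesis is preserved.

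**Any-grade comparison**, p = 35% in Arm 2 and 15% in BSC, power by exact enumeration of the Fisher test:

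| b | Arm 2 reported | BSC reported | Difference (points) | Power |
|---|---|---|---|---|
| 0 | 35.0% | 15.0% | 20 | 89% |
| 10% | 41.5% | 23.5% | 18 | 75% |
| 30% | 54.5% | 40.5% | 14 | 52% |
| 40% | 61.0% | 49.0% | 12 | 42% |
| 50% | 67.5% | 57.5% | 10 | 35% |
| 70% | 80.5% | 74.5% | 6 | 22% |

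At b = 30%, Arm 2 rises by 0.30 × 0.65 = 19.5 points and BSC by 0.30 × 0.85 = 25.5 points.

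Other assumed rates behave alike. For 40% vs 20%, power is 85%, 73%, 52% and 37% at b = 0, 10%, 30% and 50%. For 20% vs 5% it is 89%, 64%, 34% and 22%.

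**Type I error.** With a common true rate of 20%, the actual rejection rate stays at 7-9% for b from 0 to 90%, below the nominal 10%.

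**Grade 3 or higher comparison.** Here b is the proportion with a baseline symptom already at grade 3 or above, which should be small. Keeping 35% vs 15%:
- b = 2% gives 36.3% vs 16.7% and power 86.5%;
- b = 5% gives 38.3% vs 19.3% and power 82.4%.

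**Laboratory grades.** No power calculation applies. Protocol 9.1.2 says that abnormalities of protocol-specified tests are derived electronically from the values and not recorded as adverse events, and SAP 7.7.2 plans no between-arm test. Carry-over here follows directly from the counting rule, with no site judgement in between; its effect is overstated incidence only.

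**The case against.** The case for leaving the plan alone has several parts.

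- **Re-reporting is not established.** Symptom carry-over requires sites to enter unchanged baseline symptoms again on later forms. Completion rules sit in a data management guidebook that is not among the documents. This stands: the symptom effect is plausible, not certain. It does not apply to laboratory values.
- **A filter already exists.** Table 44 keeps only events possibly, probably or definitely related to treatment, which should remove many unchanged symptoms. This stands for Table 44. But relatedness is an investigator judgement in an open-label trial and is tabulated for Arm 2 only, so it does not rescue Tables 42, 43, 45 and 46.
- **Eligibility limits severe baseline symptoms.** ECOG 0-1 is required, unresolved grade 2 toxicity from earlier therapy is excluded unless irreversible, and uncontrolled intercurrent illness is excluded. Disease symptoms are not capped, but this largely protects the severe comparison.
- **Both arms and baseline are shown.** Tables 45, 46, 48 and 50 cover both arms, and Tables 14-18 give baseline. A reader can compare the margins, but cannot recover which patients worsened.
- **The test has modest weight.** The objective is to assess toxicity, and Protocol 13.2 makes Fisher testing conditional. SAP 7.7.1, however, plans it outright.

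A reader might also infer that the rule makes Arm 2 look more toxic relative to BSC. With equal carry-over it does the reverse: BSC rises by more points whenever its new-event rate is lower. Nor can the baseline laboratory grades be used to argue that the Fisher test loses power, since laboratory abnormalities do not enter it.

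**Conclusion.** The point holds in this form. The SAP counts events and laboratory grades without reference to a baseline that is collected. Absolute incidence is overstated in both arms in Tables 42, 43 and 45-54: certainly for laboratory results, and for symptoms to the extent that sites re-report them. Table 44 is partly protected.

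For the any-grade Fisher comparison the difference shrinks by 1 - b. Under the assumed 35% vs 15%, power falls from 89% to 75%, 52% and 35% at b = 10%, 30% and 50%. A reader might infer that the comparison loses most of its power. That would need carry-over of roughly 40% or more, a prevalence the documents do not give. The grade 3 or higher comparison keeps about 82-87% at b = 2-5%. Type I error is not inflated.

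The size rests on the assumed rates, on equal b in both arms, and on complete re-reporting among those counted in b. Randomization supports equal baseline prevalence, but equal re-reporting is an added assumption. The primary survival analysis is not affected.

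**What to change.** **SAP 7.7.1.** For Tables 42, 43, 45 and 46 and for the Fisher tests, count an adverse event only if it is new or has a higher CTCAE grade than the patient's baseline. Use the SAP 7.1 baseline for Arm 2. For BSC, which has no first dose, state that baseline is the last assessment on or before randomization. Define Form 1.

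**SAP 7.7.2.** For Tables 47-54, which include the thyroid and coagulation tables, either count only new or worsened abnormalities or add tables of baseline against worst grade. For tests without a CTCAE grade (such as RBC, monocytes, LDH, chloride and CEA), use a shift from the normal to an abnormal category.

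Keep the present all-reported counts as supplementary tables, so that nothing is lost and results remain comparable with the group's other reports.

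The cost is SAP wording and an extra derivation from data already collected, with some departure from the usual table format. No new data or patients are needed.
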